**Need for medical treatment for control of symptoms from reflux disease:**

In order to allow for a stringent assessment of treatment failure ask the following question:

*“Do you have sufficient control of your heartburn and acid regurgitation?”*

If the answer is **No**, continue with:

*”Do you need other regular drug treatment to control your symptoms?”*

If the answer to this question is **Yes** the subject has to be classified as a **treatment failure and will be withdrawn**.

Furthermore, the subject will also be regarded as a **treatment failure** if the following occurs;

- Post-operative - post-fundoplication complaints requiring further medical actions to control symptom burden.
- Per-operative death
- Post-operative death within 30 days after surgery
- Dysphagia requiring further treatment. In case of esophageal stenosis, one dilatation is allowed.

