### 3.3.4 Exclusion criteria

Any of the following is regarded as a criterion for exclusion from the study:

1. History of esophageal, gastric or duodenal surgery predicted to influence negatively on subsequent treatment within the study.
2. Subjects with **current** or **historical** evidence of the following diseases/conditions:
  - Zollinger-Ellison syndrome
  - The primary esophageal disorders; achalasia, scleroderma and primary esophageal spasms
  - Inflammatory bowel disease.
  - Dysplastic changes in a columnar lined esophagus.
  - Any condition associated with abnormal absorption in the GI tract.
  - Significant cardiovascular, pulmonary, pancreatic, renal or liver diseases as judged by the investigator to interfere with the evaluation of the study.
  - Malignant disease except of minor superficial skin disease.
  - Current unstable diabetes mellitus. Stable diabetics controlled on diet, oral agents or insulin are acceptable.
  - Cerebral vascular disease, such as cerebral ischemia, infarction, haemorrhage or embolus as judged by the investigator.

3. Contraindication to the study drug, e.g. known or suspected allergy to esomeprazole and any other constituents of the formulation. Known hypersensitivity to substituted benzimidazole.
4. Pregnancy or lactation.
5. Child-bearing potential (female subjects must be post-menopausal, surgically sterilized or using medically accepted contraceptive measures during the study period as judged by the investigator).
6. Any significant “alarm symptoms” such as unintentional weight loss, recurrent vomiting, recurrent dysphagia, anaemia, haematemesis, melaena, jaundice or any other sign indicating serious or malignant disease.
7. Need for concomitant therapy with:
  - per oral anticholinergics and other drugs having anticholinergic co-effects such as tricyclic and tetracyclic antidepressive drugs
  - motility activators (prokinetic drugs) – except for operated subjects between visit 5 and visit 6 for treatment of post-operative intestinal paralysis.
  - prostaglandin analogues
  - NSAIDs (except for intermittent usage)
  - ASA (except for 165 mg daily or less for cardiovascular prophylaxis and for intermittent usage)
  - anticoagulants
  - PPI (other than study medication),
  - H2RA
8. Use of any other investigational compound or participation in another clinical trial within 28 days prior to entry of the study.
9. Previous participation in this study.

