### **3.3.5 Discontinuation of subjects from treatment or assessment**

#### **3.3.5.1 Criteria for discontinuation**

Subjects may be discontinued from study treatment and assessments at any time, at the discretion of the investigator(s). A subject may, however, continue the study under exceptional circumstances (e.g. if continuation of study treatment or follow-up actions are necessary for the subjects safety and well-being, and the continuation of the study is not expected to be associated with any risk or discomfort for the subject). Specific reasons for discontinuing a subject from this study are:

1. Withdrawal of informed consent
2. Unwillingness to continue the study or lost to follow-up.
3. Any unacceptable adverse event, including laboratory result or physical findings, as judged by the investigator
4. Any “alarm symptoms” which, in the investigator’s judgement, requires treatment outside this protocol.
5. Continuous need for/intake of drugs listed under Section [3.3.4](#) criteria 7.
6. Protocol non-compliance as judged by the investigator
7. Classified as treatment failure
8. Pregnancy
9. Incorrect enrolment or randomization of subject
10. Other reason specified by the investigator.

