**Need for medical treatment for control of symptoms from reflux disease:**

In order to allow for a stringent assessment of treatment failure ask the following question:

*“Do you have sufficient control of your heartburn and acid regurgitation?”*

If the answer is **No**, continue with:

*“Do you need other regular drug treatment to control your symptoms?”*

If the answer to this question is **Yes**, the subject has to be classified as a **treatment failure and will be withdrawn**.

If the answer to this question is **Yes** and one dilatation has been done, then the subject is a **treatment failure and will be withdrawn**.

Furthermore the subject will also be regarded as a **treatment failure** if the following occurs;

- Post-operative - post-fundoplication complaints requiring further medical actions to control symptom burden
- Per-operative death
- Post-operative death within 30 days after surgery
- Dysphagia requiring further treatment. In case of esophageal stenosis, one dilatation is allowed.

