### **6.2.3 Statistical analyses**

The two treatment groups will be compared regarding the primary endpoint using Life Table methods for graphic presentation and a log rank test (two-sided) for statistical inference. In both the ITT and the PP analyses data will be censored in case of discontinuation due to reasons other than treatment failure. Post-operative complications, histopathology, endoscopy and symptoms are summarized using frequency tables.

For subjects randomized to the surgery group, post-operative complications during the first month after surgery will be assessed descriptively. Quantitative data on post-operative complications will be tabulated with Mean, SD, min and max. For post-operative complications data with nominal or ordinal outcome, the number of subjects and relative frequency distribution will be presented.

Histopathological changes will be assessed by frequency tabulation by treatment group and visit.

The number of endoscopic and/or symptomatic relapses at clinical visits will be presented by visit and treatment group with frequency tables. Mean, SD, min and max, both combined and separately.

Number of endoscopic and/or symptomatic relapses between visits will be presented by time period (subject year) and treatment group with frequency tables. Mean, SD, min and max, both combined and separately.

GI symptoms associated with GERD over time will be presented by visit and treatment in frequency tables and as number and proportion of subjects with no symptoms.

The percentage of 24 hr intragastric pH  $\leq 4$  will be presented using descriptive methods (Mean, SD) by visit and treatment group.

Symptom Association Probability (SAP) will be presented using descriptive methods (Mean, SD) by visit and treatment group.

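### Regular acid suppression after surgery can be counted as a treatment failure or censored, because the failure definition, question order, discontinuation reasons and censoring rule are not reconciled

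*Protocol*

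**What the plan says.** **Definition.** The surgical-arm failure text appears in the synopsis, Section 4.1 and Section 6.2.2 under the lead line "Need for medical treatment for control of symptoms from reflux disease". Two scripted questions follow. The first is "Do you have sufficient control of your heartburn and acid regurgitation", with no qualifier about being off medication. Only a No leads to the second, "Do you need other regular drug treatment to control your symptoms", and a Yes there is failure. Further failure events are then listed separately: perioperative death, dysphagia needing treatment, and "post-fundoplication complaints requiring further medical actions to control symptom burden". None names regular PPI or H2RA use.

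**Discontinuation.** Section 3.3.5.1 lists as reason 5 "Continuous need for/intake of drugs listed under Section" 3.3.4, criterion 7. That criterion covers H2RA and the entry beginning "PPI (other than study medication", along with drugs unrelated to reflux. Reason 6 is non-compliance. Reason 7 is "Classified as treatment failure". No order of precedence is given.

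**Analysis.** Section 6.2.3 states: "In both the ITT and the PP analyses data will be censored in case of discontinuation due to reasons other than treatment failure".

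**The concern.** Return to regular acid suppression is the central way in which surgery fails in a ten-year comparison of the two strategies. The lead line treats it as the event, the script can miss it, and the discontinuation list offers a code for the same facts that leads to censoring. The trial is open (Section 3.4.4.1) and the investigator picks the reason, so an event in the only formally tested endpoint can depend on which of two overlapping boxes is ticked.

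Censoring a subject because reflux drugs were restarted is informative. That subject has failed by the lead definition, yet the life-table estimate treats the remaining risk as the same as for subjects still controlled without drugs. In the surgical arm the error runs in one direction, towards longer apparent time to failure.

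**Working it through.** **1. Follow one subject through the text.** Take a surgical-arm subject who, after visit 7, starts a daily PPI bought over the counter or prescribed elsewhere, and whose heartburn is controlled on it.

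| Rule | Result |
|---|---|
| Lead line (4.1, 6.2.2) | Needs medical treatment for reflux: failure |
| Scripted questions (4.1, 6.2.2) | Yes to the first; second not asked; no failure identified |
| 3.3.5.1 reason 5 | Applies |
| 3.3.5.1 reason 6 | Can apply, since Section 3.4.5 prohibits the drug, including over the counter |
| 3.3.5.1 reason 7 | Applies if the site relies on the lead line |
| 6.2.3 | Event under reason 7; censored under reason 5 or 6, in ITT and PP alike |

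The same facts give opposite outcomes, and neither planned analysis corrects the other.

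**2. Can this arise in practice?** Section 3.4.5 expects entrants to have used long-term acid suppression. After the six-month visit, Table 1 spaces scheduled visits six months apart to year 5. In Table 2 clinic visits are then yearly, and the telephone visits between them record adverse events but neither symptoms nor concomitant medication. The calls to discontinued subjects at 5 and 10 years (Section 3.1) ask about current GERD treatment but are not tied to the primary endpoint.

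**3. Reproduce the planning figure.** Section 6.1 gives 275 per arm, success of at least 70% in each arm and a precision of 8 percentage points. The 95% half-width is 1.96 × √(2 × 0.70 × 0.30 / 275) = 0.0766, or 7.7 points (8.0 with a continuity correction of 1/275). The stated figure is reproduced.

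**4. Illustrate the effect.** Let f be the share of *all* surgical failures censored through this gap. The Protocol gives no value for f, so it is an assumption. If f is constant over time and the medical arm has no similar loss, the apparent surgical success is S^(1−f), where S is the true five-year success.

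| f | S = 70% | Gain (points) | S = 80% | Gain (points) |
|---|---|---|---|---|
| 0.1 | 0.70^0.9 = 72.5% | 2.5 | 81.8% | 1.8 |
| 0.2 | 0.70^0.8 = 75.2% | 5.2 | – | – |
| 0.3 | 0.70^0.7 = 77.9% | 7.9 | 85.5% | 5.5 |

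At S = 70% the gain reaches 8 points when f = 1 − ln(0.78)/ln(0.70) = 0.30. At S = 80% this needs f = 0.43.

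**The case against.** A reader might infer that crossover to medication simply disappears from the primary endpoint. The Protocol does not support that, for three reasons.

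- **The lead line.** It makes need for medical treatment the failure and presents the questions as a way to assess it stringently. A site can therefore code this subject as reason 7. Reason 5 also has an evident other purpose, because criterion 7 includes NSAIDs, anticoagulants and anticholinergics.
- **The symptom route.** Section 3.1 tells subjects with moderate to severe symptoms on at least three consecutive days to contact the clinic, where the failure questions are asked. A subject who does so before medicating, and reports insufficient control and a need for regular drugs, is counted.
- **The controls on drug use.** PPI and H2RA are prohibited, postoperative on-demand esomeprazole ends at visit 7, and all medication must be recorded in the CRF (Section 3.4.5).

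The illustration can also be over-read. It applies f to all surgical failures, although deaths, dysphagia and other postoperative complaints do not pass through the first question. If, as an assumption, two thirds of failures were reflux-drug failures, f = 0.3 would require 0.3 / (2/3) = 45% of those to be lost. It also sets the loss in the medical arm to zero, although the same overlap exists there for reflux drugs other than esomeprazole and would offset part of the bias.

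These points limit the size and certainty of the loss, but they do not remove the conflict. The symptom route depends on the subject calling before medicating, and nothing tells a site which reason prevails. Mapping reasons to events could be left to the SAP, but the Protocol itself fixes the question order and the censoring rule, and a later SAP cannot recover answers to a question that was not asked.

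**Conclusion.** The conflict is real and should be fixed. Return to regular acid suppression after surgery can be an event or a censored observation, depending on how the site codes it. Where it is censored, the censoring is informative and favours surgery.

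The loss is partial and its size is unknown. The gains of 2.5 to 7.9 points for f = 0.1 to 0.3 rest on assumed values of f, a true five-year success of 70%, a share constant over time and no loss in the medical arm. They show that a moderate leak would matter against a planned precision of 8 points. A reader might take them as an estimate of the bias, or conclude that it does reach that precision, but the Protocol contains no crossover or miscoding rate that would support either reading.

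**What to change.** Reconcile the synopsis, Sections 4.1 and 6.2.2 with Sections 3.3.5.1 and 6.2.3:

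1. Ask both questions at every visit at which failure is assessed, whatever the answer to the first.
2. State for the primary analysis that regular acid-suppressive treatment taken for reflux symptoms in the surgical arm, outside the uses permitted in Sections 3.1 and 3.4.5, is a treatment-failure event. Date it at the start of intake, even if symptoms are controlled on it.
3. State that, for endpoint classification, reason 7 takes precedence over reason 5 and over non-compliance when the drug is taken for reflux. Apply the matching precedence in the medical arm for reflux drugs other than esomeprazole.
4. For data already collected, specify before database lock an analysis that reclassifies reason-5 and similar discontinuations from the CRF medication record. Report it as a sensitivity analysis beside the primary, so that the primary endpoint is not changed retrospectively in an open trial with interim analyses.

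This concerns endpoint classification only. Whether and when such subjects stop study treatment is for the sponsor to reconcile.

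**Cost.** Wording changes and a programmed derivation, with no extra visits. Section 3.4.5 already requires medication to be recorded but does not name the indication, so the indication and start date of each acid suppressant must be checked. Surgical success may look slightly lower.

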## **4.2 Screening and demographic measurements**

At visit 1, demographic data e.g. date of birth, gender and race as well as body weight and height will be recorded. Smoking and drinking habits will also be recorded.

The investigator will carry out an eligibility check to ensure that the subject has no medical abnormalities which might disqualify him/her from enrolment. Medical and surgical history including details about GERD will be obtained and a complete physical examination will be done. The physical examination will include: general appearance, cardiovascular, lungs and abdomen and vital signs (pulse, blood pressure and body weight).

## **4.3 Efficacy measurements and endpoints**

An endoscopic examination of esophagus, stomach and duodenum, will be done in each subject. Biopsy specimens will be taken in antrum, corpus, the cardiac region (grasping the Z-line) and in esophagus (see Section 4.3.4.1 and App. H). The presence of *Hp* will be assessed by biopsy examination.

### **4.3.1 Summary of efficacy objectives and endpoints**

[Table 3](#) shows how the efficacy endpoints of this study relate to the study objectives.

**Table 3 Efficacy objectives and endpoints relating to each objective**

Objective	Endpoint(s)	Summary statistic for analysis (incl. timepoint and population)	Planned analysis	Significance of results
Primary				
4.1, 4.3.2 To compare treatments with regard to treatment failure	Number of days, treatment failure (yes/no)	Median number of days  ITT population	Logrank test, and survival curves	Longer time to treatment failure indicates a more efficient treatment
Other				
4.3.3 Histopathological findings	Histological assessments .	All histological presentations will be performed for the safety population and ITT population.	No formal statistical comparison	
4.3.4 Periodic prevalence of endoscopic and symptomatic recurrences	Endoscopic relapse (LA grade C-D) between scheduled endoscopies. Symptomatic relapse between scheduled visits	Mean number of relapses per time period (subject year). ITT population	Descriptive descriptive	
4.3.4 Point prevalence of endoscopic and symptomatic recurrences	Endoscopic relapse (LA C-D) at scheduled endoscopies. Symptomatic relapse at scheduled visits.	Mean number of relapses per scheduled endoscopy visit. ITT population		
4.3.5 GI symptoms assoc. with GERD over time	Symptom assessments at clinical visits	Proportion of subjects with no symptoms ITT population	descriptive	
4.3.6 Per-operative events	Per-operative event assessments during the operation	Proportion of subjects randomized to surgery with per-operative symptoms ITT population	descriptive	
4.3.7 Post-operative symptoms and events	Post-operative symptom assessments during the first 30 post-operative days	Proportion of subjects randomized to surgery with post-operative symptoms ITT population	descriptive	
4.3.8 24 hr intragastric and intraesophageal pH	% of time with intragastric and intraesophageal pH $\leq$ 4	ITT population	Descriptive	
4.3.8 Symptom Association Probability (SAP)	Association between symptoms and reflux episodes	ITT population	Descriptive	

The methods for collecting efficacy data are presented below.

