#### **4.3.7 Post-operative symptoms and events**

##### **4.3.7.1 Methods of assessment**

The method of assessment of short term (< 30 days) post-operative lapse and symptoms will be made by the investigator in a standardized manner and recorded in the CRF at visit 6 for operated subjects to ensure a smooth post-operative recovery.

- Post-operative hospital stay (days).
- Abdominal infection.
- Other abdominal complications.
- Pulmonary infection.
- Other pulmonary complications.
- Bleeding
- Other complications
- In hospital post-operative death
- Other post-operative symptoms

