### **6.2 Statistical evaluation**

#### **6.2.1 Methods of statistical analysis**

A comprehensive Statistical Analysis Plan will be prepared before unblinding the data, or in instances where the data are not blinded, database lock.

Both Intention To Treat (ITT) and Per Protocol (PP) analyses will be made for the primary variable. Secondary variables will be analysed for the ITT population only. In the ITT analyses all randomized subjects will be included, except subjects who are randomized into medical treatment and who have taken no dose of study drug, or subjects who are randomized to laparoscopic fundoplication and who refuse to undergo the operation. The PP population will include subjects with no major protocol violations, including the violation of entry criteria (the nature and reasons for these protocol violations will be defined and documented before

database lock). Subjects eligible for safety evaluation are those who take at least one dose of the study drug and for whom post-dose information is available.

The two treatment groups will be compared regarding the primary endpoint using Life Table methods for graphic presentation and a logrank test for statistical inference.

For each GSRS and QOLRAD dimension, the individual score at each assessment is calculated as the average score for the items included in the dimension. If there are missing items in the questionnaires, the mean of the completed items in one dimension will be imputed to substitute the missing item provided that more than 50% of the items in one dimension are completed.

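### Per-operative and 30-day post-operative proportions are based on the ITT surgical arm, which can include subjects who were never operated on; the denominator should be subjects in whom the operation was started

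*Protocol*

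**What the plan says.** Protocol Table 3 defines the two operative summaries in parallel: "Proportion of subjects randomized to surgery with per-operative symptoms", with the ITT population named in the same cell, and "Proportion of subjects randomized to surgery with post-operative symptoms ITT population". Both are labelled descriptive.

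Section 6.2.3 keeps the as-randomized basis for the post-operative part: "For subjects randomized to the surgery group, post-operative complications during the first month after surgery will be assessed descriptively". Categorical results there are to be given as numbers and relative frequencies.

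Section 6.2.1 defines ITT as all randomized subjects with two exceptions. The one for the surgical arm is "subjects who are randomized to laparoscopic fundoplication and who refuse to undergo the operation". No other reason for not being operated on removes a subject from ITT.

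The data come from operated subjects only. Section 4.3.6.1 lists complications of the operation itself, and section 4.3.7.1 has the post-operative course "recorded in the CRF at visit 6 for operated subjects".

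**The concern.** Bleeding, perforation or pneumothorax during an operation can occur only in someone who is operated on, and the same holds for complications in the following 30 days. The numerator and the data collection are therefore confined to operated subjects, while the stated denominator is a randomized set that need not be. A subject in the denominator without an operation contributes to the bottom of the fraction and never to the top.

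These rates describe the main risk of the comparator. Section 8.2 names post-operative morbidity and complications as the risk attached to surgery. Under section 4.4.2.2, the listed post-operative symptoms are recorded as adverse events only if they lead to discontinuation, and are reported as serious if they meet those criteria. The Table 3 and section 6.2.3 summaries are thus the main place where the remaining complications appear, and a reader will take the figures as risk per operation.

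**Working it through.** **Plan's own figure.** The protocol gives no operative event rate and no expected number of unoperated subjects, so there is nothing to reproduce on this point. Its only design figure, the 8-point precision in section 6.1, concerns five-year success and does not bear on the denominator.

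**Step 1: who is in the denominator.** Table 3 says randomized to surgery, ITT. Section 6.2.1 removes refusers. The denominator is therefore randomized to surgery minus refusers.

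**Step 2: can that set contain unoperated subjects?** Yes.
- Sections 3.1 and 3.4.2 allow up to three months between randomization and surgery.
- Section 3.3.5.1 lists reasons for discontinuation that are not refusal of surgery, including an unacceptable adverse event, alarm symptoms, pregnancy, loss to follow-up and incorrect randomization.
- Section 3.3.5.3 discontinues incorrectly randomized subjects from further study treatment.
- Whether withdrawal of consent during the wait counts as refusing the operation is not stated.

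**Step 3: does another defined set equal operated subjects?** No. The safety set in section 6.2.1 is defined by intake of study drug, and the per-protocol set by absence of major violations.

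**Step 4: direction and size.** Let u be the share of the surgical arm not operated on and s the share of those who refused. If the remaining unoperated subjects are counted without an event, then

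reported rate / rate per operated subject = (1 − u) / (1 − s·u).

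The ratio cannot exceed 1, and it equals 1 when s = 1. All values of u and s below are assumptions, as is the 10% rate per operated subject used for the percentages.

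| u | s = 0 | s = 0.5 | s = 0.8 | s = 1 |
|---|---|---|---|---|
| 5% | 0.950 (9.5%) | 0.974 (9.7%) | 0.990 (9.9%) | 1.000 (10.0%) |
| 10% | 0.900 (9.0%) | 0.947 (9.5%) | 0.978 (9.8%) | 1.000 (10.0%) |
| 15% | 0.850 (8.5%) | 0.919 (9.2%) | 0.966 (9.7%) | 1.000 (10.0%) |

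Example: u = 0.10 and s = 0.5 give 0.90 / (1 − 0.05) = 0.947, so 10% is reported as 9.5%.

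The column s = 0 is what dividing by all subjects randomized to surgery would give. Under the protocol's ITT it arises only if none of the unoperated subjects refused.

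**The case against.** **Refusers are already out.** From the first words of the Table 3 cell, a reader might infer that the rates divide by everyone randomized to surgery and that operative risk is materially understated. The documents do not support that. The cell goes on to specify ITT, and section 6.2.1 takes refusers out, which brings the set close to the operated subjects. This stands and limits the point to subjects unoperated for other reasons.

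**The phrase may only name the arm.** Table 1 uses the same as-randomized wording as a footnote to the surgery visit and the post-operative assessment. An unoperated subject has no operative record, and no section says that a missing record is scored as no event. An analyst might therefore divide by operated subjects anyway. That is possible, but Table 3 states a proportion and a population, and read literally these include the unoperated. The ambiguity is a reason to settle the wording.

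**It belongs in the statistical analysis plan.** A denominator left open could be settled there. Here the protocol fixes one, and it does not match the data collection.

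**The effect is trivial.** Suitability for surgery is required at enrolment and again at randomization (sections 3.3.2 and 3.3.3), which makes early unfitness less likely. At a 10% rate in about 260 subjects (both assumed), the standard error is √(0.10 × 0.90 / 260) = 1.9 percentage points, so even the shifts of 0.5 to 1.5 points in the column s = 0 lie within one standard error. No test depends on these summaries, and operative and 30-day deaths count in the primary endpoint (section 4.1). All of this stands and keeps the point minor. It does not make the denominator right, because the shift is systematic and always in the same direction.

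**Conclusion.** The point holds as a minor one. The protocol bases both operative proportions on the ITT surgical arm. That set excludes refusers but, read literally, retains subjects unoperated for any other reason. Counting them can only lower the reported operative risk.

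The size cannot be determined from the documents. With 5% to 15% unoperated and at least half of them refusers, both assumed, the reported rate is 0.92 to 1.00 times the rate per operated subject. It is unbiased if every unoperated subject refused. A material understatement of operative risk is not shown. The primary comparison is unaffected.

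**What to change.** In both operative rows of Table 3, and in the post-operative sentence of section 6.2.3, make the denominator all subjects in whom the operation was started. Starting rather than completing the procedure is the right boundary, because section 4.3.6.1 records completion separately and an abandoned operation can still cause complications. Report alongside it the number randomized to surgery but not operated on, with reasons, refusal being one of them.

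No new data are needed: the per-operative record, the visit 6 assessment and the reason for discontinuation (section 3.3.5.4) are already collected. The rates would also no longer depend on how ITT is defined. The cost is a wording change in descriptive tables, and the stated rates may become slightly less favourable to surgery.
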